Despite widespread utilization of NMB during cardiac surgery, very little is known about residual neuromuscular blockade in patients following cardiac surgery. A recent large, retrospective study of a non-cardiac surgical database has linked intermediate-acting neuromuscular blockade and postoperative pulmonary complications in a dose-dependant manor.⁶ Patients undergoing cardiac surgery are even more susceptible to the detrimental effects of residual neuromuscular blockade than in non-cardiac surgical patients, however no recent clinical studies have been directed at this population. The few studies that have examined NMB in cardiac surgical populations have served to shift routine practice away from older, long-acting NMB agents (e.g. pancuronium) toward the intermediate-acting agents (e.g. rocuronium or cisatracurium) commonly used during non-cardiac surgery.¹²⁻¹⁶ Yet, cardiac surgical patients experience physiologic conditions not associated with non-cardiac surgery, such as exposure to hypothermic cardiopulmonary bypass which is known to decrease muscle strength substantially

even in the absence of NMB.^{17,18} Additionally, the clinical effects of NMB may be intensified during hypothermia via complex pharmacokinetic and pharmacodynamic interactions not yet fully understood.¹⁹⁻²⁴ Cardiac surgical patients may also be more susceptible to the harmful effects of residual neuromuscular blockade due to significant comorbidities predisposing them to postoperative pulmonary complications.²⁵⁻²⁸ Concern over detrimental effects of NMB have led some to call for minimizing or eliminating the continuous use of NMB during cardiac surgery, as acceptable surgical conditions may be achieved with adequate depth of anesthesia and blunting of the physiologic response to surgery.^{29,30} Given the traditional role of neuromuscular blockade in the management of cardiac surgical patients, prospective data is needed to determine the effect of NMB in cardiac surgical patients as well as the surgical tolerability of protocols that minimize intraoperative paralysis.

The proposed prospective, randomized trial will assess the impact of neuromuscular blockade on early (≤ 72 hours post-ICU admission) postoperative respiratory complications. This clinical study will prospectively investigate two groups of patients undergoing elective cardiac surgery at the University of Chicago. In the experimental group, a very short-acting depolarizing NMB (succinylcholine) will be used for tracheal intubation and no other subsequent muscle relaxants throughout surgery. In the control group, an intermediate-acting non-depolarizing NMB (cisatracurium) will be used throughout the intraoperative period (our standard practice) and will be re-administered to maintain a moderate to deep level of muscle relaxation until the conclusion of surgery. Both groups will be monitored with peripheral nerve stimulators (ulnar and facial nerve) throughout the intraoperative period and immediate postoperative period. Residual neuromuscular blockade during the immediate postoperative period will be assessed in both groups objectively and subjectively.

Recent clinical studies support the use of intraoperative acceleromyography for titration of NMB based on the motor response of nerve stimulation.³¹ Since during cardiac surgery, anesthesiologists have limited access to the patient's arms due to patient positioning, both the adductor pollicis and orbicularis oculi sites will be monitored with a TOF-Watch to provide for correlation as well as redundancy in the event of intraoperative disturbance of the adductor pollicis site due to surgeon positioning.

The primary outcome to be examined is the composite event of a postoperative pulmonary complication linked to residual NMB. Surgical tolerability (assessed via specifically designed cardiac surgeon rating scale and examination of undesired patient movement during anesthesia) and subjective/objective signs of postoperative weakness (patient questionnaire, neuromuscular blockade monitoring) are the secondary outcomes to be assessed.

Methods

A prospective, randomized protocol was designed to assess the impact of low/single dose NMB on the incidence of early respiratory complications in cardiac surgery. Reported incidence of respiratory complications after cardiac surgery ranges from 0.5-30% depending upon the particular complication and population subset being examined. The current study focuses on a pre-defined composite measure of respiratory complications that are potential sequelae of NMB-associated effects on respiratory muscle weakness. This primary outcome measure will include the following and will be determined through prospective observation for 72 hours following admission to the intensive care unit (ICU) postoperatively. (See "Data Collection: Respiratory Complications")

1. Failure to extubate within 24 hours of ICU admission time
 - Determined via documentation of extubation time

2. Need for tracheal re-intubation (≤ 72 hours post-ICU admission)
 - Determined via documentation of respiratory therapy/intubation events
3. Pneumonia
 - Defined by radiologist report or ICU attending assessment of new or progressive pulmonary infiltrate on chest x-ray *AND*
 - Clinical findings suggesting systemic infection (fever $>38^{\circ}\text{C}$ or $<36^{\circ}\text{C}$ *OR* WBC count $>12,000/\text{mm}^3$ or $<4,000/\text{mm}^3$) *OR* antibiotic therapy *OR* positive respiratory cultures/purulent sputum
4. Pulmonary aspiration
 - Diffuse infiltrates or consolidation of dependant lung segments on chest x-ray consistent with aspiration
 - *AND* clinical findings consistent with aspiration pneumonitis, including increasing oxygen requirements, suspected aspiration or increased work of breathing
5. Need for noninvasive respiratory support with CPAP or BiPAP therapy
 - Documented use required during first 72 hours post-ICU admission
 - Composite scoring of respiratory events does not include continuation of CPAP therapy as prescribed preoperatively for known obstructive sleep apnea (OSA)
 - Includes escalation of therapy (BiPAP treatment when previously CPAP only was needed)
6. ARDS (mild, moderate or severe) (≤ 72 hours post-ICU admission) based on Berlin definition:
 - Bilateral opacities on chest x-ray consistent with pulmonary edema
 - Arterial blood gas and ventilator setting evidence of $\text{PAO}_2/\text{FiO}_2$ ratio ≤ 300

- Not fully explained by cardiac failure or fluid overload
7. Mortality attributed to respiratory event (≤ 72 hours post-ICU admission)
- Hypoxic or hypercarbic respiratory arrest

Secondary outcomes in the study will be:

1. Surgical Tolerability

- Measured by a designed instrument that will be completed by the surgeon and anesthesia staff and will include reporting of the following (See “Data Collection: Surgical Tolerability”)
 - Patient movement: Major (limb movement, coughing on ventilator), minor (diaphragm movement), none
 - Movement interfering with surgical progress: Yes, no
 - Surgical conditions: Excellent, good, poor
 - Total dose supplemental propofol required for suppression of movements
 - BIS recorded during patient movement

2. Weakness (See “Data Collection: Postoperative”)

- Blinded assessment of patient experience of weakness or respiratory difficulties on postoperative survey (See “Postoperative Survey”)

Study Risk and Benefits

When continuous muscle relaxation is omitted, there is a risk of movement under anesthesia (e.g. coughing, limb muscle movement), which may interfere with surgery. Movement under anesthesia occurs occasionally even when muscle relaxation is provided continuously (during standard of care), but in the absence of muscle relaxation (non-standard of care), these movements may be more pronounced. Other anesthesia medications (i.e. anesthetic agents,

analgesic agents) are provided when muscle relaxation is not being administered to minimize these risks. In our study, midazolam and fentanyl (standard of care medications) will be administered in doses to avoid the potential for inadvertent movement. In the low dose muscle relaxant group, inadvertent patient movement will be treated with additional anesthesia with propofol, increasing the dose of volatile anesthetic, administering pain medication or if necessary for patient safety, administering muscle relaxants as required (i.e. reverting to standard of care). The risk of movement under anesthesia when low dose muscle relaxant is used is reasonable because providing anesthesia without muscle relaxation is an established technique used for other types of surgery (e.g. non cardiac).

As muscle relaxation has been associated with harmful effects (e.g. postoperative pulmonary complications), the use of low doses has some potential benefit. Results from this study may help future patients having cardiac surgery by providing guidance to the best way to conduct anesthesia to minimize respiratory complications.

Monitoring of Safety

There will be ongoing (case by case) review of adverse events and safety information between the principal investigator and co-investigators and any events will be addressed. Unanticipated problems requiring a revision to the protocol will be submitted to the IRB for review. A Data Safety Monitoring Board has been convened and will review the results early in the study as well as halfway through enrolment to address any safety concerns. A continuing review with examination of preliminary data will be conducted after 50 patients have been recruited.

Unanticipated problems (i.e. unexpected events that are related or possibly related to participation in the research that suggest that the research places subjects or others at risk of unknown harm or increased frequency of harm) will be reported to the IRB within 10 working

days of the investigator's knowledge of the event. In the event of a fatal or life-threatening unanticipated problem, enrolment will be halted and the IRB chair notified by phone immediately. A major deviation from the protocol will be reported within 10 working days via the "Unanticipated Problem" form. A minor deviation will be summarized at the time of continuing review on the "Continuing Review Form".

Power Calculation:

Previous studies of respiratory complications after cardiac surgery have suggested incidence rates ranging from 0.5-30%.^{26,27,33-35} Many of these studies include atelectasis and pleural effusions in their composite calculation of respiratory complications, which are problematic because of diagnostic difficulty and less clear relationship to NMB use. The current study will focus solely on the respiratory complications previously defined. Assuming this composite has a potential incidence of 20% and that the effect size is 0.5, a total of 47 patients will be required in each arm to achieve a power of 80% with a $p=0.05$. A total of 100 patients will be recruited to account for crossover.

Inclusion Criteria

All patients >18 years old undergoing elective cardiac surgery (coronary artery bypass grafting [CABG], valve replacement or CABG + valve replacement) requiring cardiopulmonary bypass at the University of Chicago with one of two surgeons ([name] or [name]).

Exclusion criteria

Emergency surgery, extremes of age (<18 or >90 years), previous cardiac surgery, clinical contraindications to succinylcholine or cisatracurium, anticipated difficult tracheal intubation, preoperative mechanical ventilation, preoperative pharmacologic/mechanical hemodynamic support.

Study Protocol

Institutional Review Board approval will be obtained and the study will be registered with www.clinicaltrials.gov prior to commencement. All patients enrolled in the study will be randomized to either a standard protocol (Group CIS) or the single-dose NMB protocol (Group SUX) (See “Intraoperative Protocol”). All study and anesthetic drugs will be administered by the anesthesia care team. The neuromuscular blocking agents being studied will be dispensed by the operating room pharmacy, as is routine, and drawn up in the operating room for intravenous administration. ICU providers and surgeons will be blinded to the study group assignment, and intraoperative and postoperative care will otherwise be routine.

No compensation will be provided to study participants. Patients will be identified by review of operative room schedules and consent will occur prior to the standard preoperative interview. The data set created from study information will be maintained following study completion but all patient identifiers will be deleted. This will be maintained for a minimum of 6 years. Consent forms with patient identifying information will be held in a locked file in a locked office for a minimum of 6 years. Randomization will be performed by computer generation. Data analysis will be performed on an intention to treat basis.

Data Collection

The investigators will collect the following data points.

Patient Factors – See “Data Collection: Preoperative”

Intra-operative Factors – See “Data Collection: Intraoperative and Data Collection: Surgical Tolerability”

Post-operative factors – See “Data Collection: Postoperative, Data Collection: Respiratory Complications, Data Collection: Postoperative Survey”

Intraoperative Protocol

Patients are to receive the same standardized doses of medications as a total for the case. Induction/maintenance medications are to be administered with induction or prior to CPB, as hemodynamics allow. IV boluses of phenylephrine (100mcg), vasopressin (1 unit), ephedrine (10mg) or norepinephrine (8mcg) may be administered as required.

Induction/maintenance:

- Midazolam 0.1mg/kg
- Fentanyl 15 mcg/kg
- Isoflurane: titrated to maintain BIS <55 or prevent patient movement, minimum of 0.6% while on CPB
- Propofol bolus (0.2-0.5 mg/kg): as needed for patient movement
- Propofol infusion started (25-50 mcg/kg/min) at “drapes down”, Isoflurane stopped
- Appropriate antibiotic administration according to hospital protocol

Mechanical Ventilation Parameters

- Tidal volume 6mL/kg of ideal body weight: male IBW = $50 + 2.3(\text{height in inches} - 60)$, female IBW = $45.5 + 2.3(\text{height in inches} - 60)$
- RR appropriate to maintain pCO₂ between 35-45 mmHg
- FiO₂ 100% intraoperatively
- PEEP 5

Neuromuscular Blockade

Group SUX	Group CIS

• Succinylcholine 1mg/kg• No additional muscle relaxants for case	
• Cisatracurium 0.2mg/kg• Supplemental cisatracurium as dictated by peripheral nerve stimulator on the hand to maintain 1-2 twitches• Last dose given at sternum closure

TOF monitoring

- Place TOF-Watch monitor on left arm (ulnar nerve monitoring) and along facial nerve (orbicularis oculi monitoring)
- Left arm will be secured at the patient’s side with the TOF-Watch hand stabilizer in place while allowing the hand/thumb free movement for measurement with TOF-Watch
- Assess TOF at times indicated on intraoperative data collection sheet
- Continue to monitor TOF ratio in group SUX even after initially returns to 100% and record changes during CPB/hypothermia

Data Collection: Preoperative

Group Assignment (circle one):	Group SUX	Group CIS
MRN: _____	Height _____ cm Weight _____ kg Ideal Body Weight _____ kg	
Age: _____	Gender (circle one): M / F	
Preoperative creatinine:	_____ mg/dL	
Surgical Date (mth/day/year)	____/____/____	
Diagnosis:		
Proposed Surgery:		
Anesthesiologist (circle):	[name] [name] Other: _____	
Surgeon (circle):	[name] [name]	

	YES	NO
Pulmonary disease (long-term bronchodilator/steroid use)		

 Obstructive sleep apnea diagnosis CPAP therapy: Yes _____ cmH₂O NO _____ 		

 Active smoker (current ppd: _____) 		

 Smoking history (quit date: _____) 		
Extracardiac Arteriopathy/PVD (claudication/carotid disease/vascular surgery, >50% stenosis)		

 HTN 		

 Diabetes Mellitus 		

 History of CVA 		
Neurologic dysfunction (severely affecting ambulation or day-to-day function)		

 Preop functional status, partially dependant 		

 Preop functional status, totally dependant 		
Active endocarditis (still using antibiotics)		
Critical preoperative state (preop cardiac arrest or dialysis)		
Unstable angina (rest angina, IV nitrates, IABP)		
LV dysfunction (LVEF <30%)		

Recent MI (<90 days)		
Pulmonary hypertension (PA systolic >60mmHg)		
Isolated CABG		
Thoracic aortic surgery		
Post-infarct septal rupture		

Preop Meds		YES	NO
Cardiac	Beta-blocker		
	ACEi		
	ARB		
	Nitroglycerin		
	Diuretic		
	ASA		
	Plavix		
	Statin		
	Pulmonary	Bronchodilators	
Steroids			
Diabetes	Insulin		
	Oral hypoglycemics		
Other	Antibiotics		

Data Collection: Intraoperative

Time Point	TOF EYE	Bladder Temp (Celsius)	BIS measurement
Baseline (pre-muscle relaxant)			
Post-intubation			
Skin incision			
Sternotomy			
Heparin admin			
CPB 10 min			
CPB 30 min			
CPB 60 min			
CPB 90 min			
CPB 120 min			
CPB 180 min			
CPB 240 min			
CPB separation			
10 min post-Protamine			
Chest closure			
Drapes down			

	TIME		DATA
Induction		Initial ABG (FiO2 1.0)	
Incision		Post-Protamine ABG (FiO2 1.0)	
CPB on			
CPB off			
Chest closure			
Out of OR		Lowest CPB temp	
ICU arrival		Last OR patient temp	

Intraoperative Drug Totals			
Midazolam _____	mg	Phenylephrine _____	mcg
Fentanyl _____	mcg	Vasopressin _____	units
Cisatracurium _____	mg	Ephedrine _____	mg
Propofol _____	mg	Norepinephrine _____	mcg
		Epinephrine _____	mcg
Blood Product Units: RBC _____	FFP _____	Plt _____	Cryo _____

Data Collection: Surgical Tolerability

Surgical Tolerability Assessment Tool (to be asked of primary surgeon at conclusion of surgery):

- Did you notice patient movement? **YES / NO**
 - If yes, how severe was the movement?

MAJOR (limb movement, coughing on ventilator)

MINOR (diaphragm movement)
 - Did movement interfere with surgical progress? **YES / NO**
- How were the surgical conditions, compared to expected? (1 being poor and 5 being excellent)

1.....2.....3.....4.....5
(POOR ... GOOD ... EXCELLENT)

Patient Movement Record (to be completed by anesthesiologist)

	Clinical Scenario	BIS	Major movement (Y/N)	Interfere with Surgery (Y/N)
1				
2				
3				
4				
5				
6				

Data Collection: Postoperative

ICU arrival time:	_____ :
ICU arrival hemodynamic support:	
ICU arrival spontaneous movement/resp effort*	YES / NO
TOF assessment at 20 min	TOF EYE _____

*Observed by investigator for 20min following ICU arrival – includes any gross movement of limbs or respiratory effort

Data Collection: Respiratory Complications

Composite incidence of respiratory complication:

Document presence of any of the following conditions during the first 72 hours postoperative (i.e. from the time of admission to the ICU)

See criteria defined in protocol

	YES	NO
Failure to extubate within 24h of ICU admission		
Need for re-intubation within 72h		
Pneumonia		
Aspiration		
Unanticipated need for noninvasive respiratory support (CPAP/BiPAP) during first 72h		
ARDS (PaO ₂ /FiO ₂ ratio \leq 300)		
Mortality attributed to respiratory arrest		

Outcomes:

ICU admission date/time: _____

Tracheal extubation date/time: _____

ICU discharge date/time: _____

Hospital discharge (or death) date/time: _____

Data Collection: Postoperative Interview

To be completed with patient on Post-op Day #7. Interviewer will be blinded to the patient group.

INTRAOPERATIVE AWARENESS? YES / NO

- Do you remember any events from during your surgery, from the time you “went to sleep” to the time you were brought to the intensive care unit?

IF YES: _____

PERI-EXTUBATION WEAKNESS? YES / NO

- At the time that you had the breathing tube removed, do you remember feeling weak, having a hard time breathing or coughing, or needing your breathing supported with a machine?

IF YES: _____

- If you had a hard time breathing, do you remember why this was (CHECK ALL THAT APPLY)?
 - **DUE TO PAIN**
 - **DUE TO MUSCLE WEAKNESS**
 - **DUE TO SLEEPINESS**
 - **DUE TO FATIGUE/BEING TIRED**
 - **DUE TO SORE THROAT/MOUTH SWELLING**

LEFT ARM PROBLEMS? YES / NO

- Are you or did you have any unusual symptoms in your left arm (such as pain, numbness, tingling) since your surgery?

IF YES: _____

POSTOPERATIVE PULMONARY COMPLICATIONS? YES / NO

- Do you believe you had a breathing complication after your surgery?

IF YES: _____

References:

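### The pneumonia component accepts any reading below 36°C from ICU admission, and any antibiotic therapy, so an infiltrate with a non-infectious or routine accompaniment can count as a primary event

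*Combined protocol and SAP*

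**What the plan says.** Methods, primary outcome component 3, has two limbs joined by AND.

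- **Limb 1, the film:** "Defined by radiologist report or ICU attending assessment of new or progressive pulmonary infiltrate on chest x-ray".
- **Limb 2, one supporting finding:** a temperature or white-cell criterion, introduced as "Clinical findings suggesting systemic infection (fever $>38^{\circ}\text{C}$ or $<36^{\circ}\text{C", with further alternatives: "OR* antibiotic therapy *OR* positive respiratory cultures/purulent sputum". Any one of these is enough.

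The composite "will be determined through prospective observation for 72 hours following admission to the intensive care unit (ICU) postoperatively". The Respiratory Complications form repeats the window as "during the first 72 hours postoperative (i.e. from the time of admission to the ICU". That form has a single YES/NO line for pneumonia and refers back to the protocol for the criteria.

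Four other places bear on how limb 2 works in this population:

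- The introduction names "exposure to hypothermic cardiopulmonary bypass" as a condition that sets cardiac surgical patients apart, and the inclusion criteria require bypass.
- The intraoperative form records bladder temperature through the case, the lowest bypass temperature and "Last OR patient temp". No ICU temperature field appears on the postoperative forms.
- The Intraoperative Protocol lists antibiotics under hospital protocol among the medications for all patients.
- The preoperative form has entries for antibiotics as a current medication and for active endocarditis under treatment. Neither is an exclusion.

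**The concern.** On its plain wording, limb 2 is met by one reading below 36°C taken as the patient reaches the ICU. No repeat reading, minimum duration or rewarming condition is asked for. A patient who arrives slightly cold, rewarms uneventfully and has a new opacity reported as an infiltrate within 72 hours is a primary event, even with a normal white-cell count and no sputum or culture finding. The antibiotic criterion has the same gap: no indication or start time is required, so a routine course, or one begun before surgery for another reason, could satisfy it.

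Two neighbouring components do remove innocent explanations. Component 5 leaves out continuation of CPAP prescribed before surgery, and component 6 leaves out opacities fully explained by cardiac failure or fluid overload. Component 3 has no counterpart.

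The Power Calculation section also criticises composites that include atelectasis and effusions, "which are problematic because of diagnostic difficulty and less clear relationship to NMB use". A non-specific opacity paired with a non-specific accompaniment comes close to that kind of event. Bypass and protocol antibiotics are common to both arms, so such events would add noise to the comparison the trial is meant to make.

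**Working it through.** **1. What the rule allows.** Pneumonia = infiltrate AND (temperature >38°C or <36°C, OR WBC >12,000 or <4,000/mm³, OR antibiotic therapy, OR positive cultures/purulent sputum). The window is 0 to 72 hours from ICU admission. A first ICU reading below 36°C lies inside the window and satisfies limb 2 alone. So does any antibiotic given in the window.

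**2. What the documents give on frequency.** Nothing. There is no ICU-arrival temperature, rewarming target or share of patients below 36°C. Nor do they say whether the protocol antibiotics continue into the ICU or would be counted. The size can only be illustrated.

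**3. The plan's own figures.** Power Calculation gives a composite incidence of 20%, an effect size of 0.5 and 47 per arm for 80% power. The scale of 0.5 is not stated; I read it as a halving, 20% versus 10%. The pooled two-sided formula is

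n = [1.96·√(2·p̄·(1−p̄)) + 0.8416·√(p₁(1−p₁) + p₂(1−p₂))]² / (p₁−p₂)²

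With p̄ = 0.15 this is [1.96·√0.255 + 0.8416·√0.25]² / 0.01 = 199 per arm, so 47 is not reproduced under this reading. That is a separate matter, and nothing below depends on it except the power column.

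**4. Effect of false events.** Let f be the share of patients without a true event who are counted only through limb 2's non-specific routes. Assume f is equal in both arms.

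Observed rate = p + (1−p)·f

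- f = 5%: 0.20 + 0.80 × 0.05 = 0.240; 0.10 + 0.90 × 0.05 = 0.145; ratio 0.145/0.240 = 0.604.
- f = 10%: 0.20 + 0.80 × 0.10 = 0.280; 0.10 + 0.90 × 0.10 = 0.190; ratio 0.190/0.280 = 0.679.

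With 50 patients per arm, false events = f × (50 × 0.80 + 50 × 0.90) = 85f.

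| f (assumed) | Control | Experimental | Risk ratio | Difference (points) | False events per 100 | Power at 47 per arm |
|---|---|---|---|---|---|---|
| 0 | 20.0% | 10.0% | 0.50 | 10.0 | 0 | 27.1% |
| 2% | 21.6% | 11.8% | 0.55 | 9.8 | 1.7 | 24.4% |
| 5% | 24.0% | 14.5% | 0.60 | 9.5 | 4.3 | 21.3% |
| 10% | 28.0% | 19.0% | 0.68 | 9.0 | 8.5 | 17.5% |

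**5. Can it be repaired afterwards?** Not from the forms. Pneumonia is one YES/NO entry, the criterion met is not recorded, and the forms hold no ICU temperature. Events resting on one reading or on routine antibiotics could be found only by going back to the charts.

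**The case against.** The strongest reply is that the problem may be rare.

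- **Several things must coincide.** The infiltrate must be new or progressive and called by a radiologist or ICU attending. A reading below 36°C must also occur, and f counts only patients who meet no other criterion. This stands: a reader might infer that cooling after bypass is expected and so turns an infiltrate alone into an event, but the documents support neither part. They make early cooling plausible and give no ICU temperature, and the second finding is still required.
- **The lead-in asks for findings that suggest systemic infection, and ICU providers are blinded.** An assessor could therefore discount a patient who is merely rewarming. This stands in part. The lead-in is followed by bare thresholds, so two careful assessors could score the same patient differently. It also does not clearly govern the antibiotic criterion.
- **The illustration may overstate.** The 20% is assigned to the composite as defined, so it may already contain such events, and the values of f have no source. Both points stand. The absolute difference moves by only 0.5 to 1.0 point at f = 5% to 10%.
- **Dilution toward no difference is not certain.** It needs similar false-event rates in both arms. Shared bypass and the blinding of ICU providers make that reasonable; the documents do not show it.
- **Tightening the temperature rule alone might change little,** because the same patient could still qualify through antibiotics. This is correct, and it is why both criteria need attention.
- **Calling atelectasis an infiltrate is a film-reading error.** True, and no limb 2 rule cures it. A specific limb 2 would still limit its effect on the primary outcome.

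**Conclusion.** The concern holds as a defect in a stated outcome rule. The wording of component 3 lets one early low temperature, or any antibiotic therapy, complete a pneumonia event in the primary composite, and the form keeps no trace of which criterion was used. This follows from the text and needs no assumption.

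The size is unknown. The risk ratios of 0.60 and 0.68 rest on three assumptions: true rates of 20% and 10%, misclassification of 5% or 10% of non-event patients, and equal misclassification by arm. They show direction and scale, not an estimate. A reader should not conclude that most patients arrive cold, that bias toward no difference is established, or that the pneumonia component is invalid as a whole.

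With only 100 patients, about four false events (f = 5%) are enough to matter, and the correction is inexpensive. It should be made.

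**What to change.** In component 3, and in matching words on the Respiratory Complications form:

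1. Count a temperature below 36°C only if it is recorded after the patient has first reached 36°C in the ICU.
2. Count antibiotic therapy only when it was started or changed for suspected respiratory infection, not when it is routine prophylaxis.
3. Replace the single pneumonia YES/NO with a YES/NO plus tick boxes for each limb 2 criterion met.
4. Prespecify a sensitivity analysis of the composite that excludes pneumonia events resting on low temperature or antibiotics alone. A patient with another qualifying component stays an event.

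A fixed interval between the reading and the film could be added, but the documents offer no basis for choosing its length, so I do not propose one. The changes concern scoring only and alter no treatment.

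The cost is a few lines of text and some chart review, since the forms hold no ICU temperatures. A true early pneumonia whose only sign is a low temperature before rewarming would be missed; the fever, white-cell, culture and sputum criteria remain, as does antibiotic treatment begun for a suspected respiratory infection.

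### The forms cannot yield the propofol dose given to suppress movement: the tolerability instrument has no dose field, and the only propofol field is one undivided intraoperative total

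*Combined protocol and SAP*

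**What the plan says.** Surgical tolerability is the first secondary outcome. The protocol describes it as "Measured by a designed instrument that will be completed by the surgeon and anesthesia staff and will include reporting of the following", points to the form headed Data Collection: Surgical Tolerability, and lists five items. One of them is "Total dose supplemental propofol required for suppression of movements".

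That form has two parts:

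- The surgeon's part, "Surgical Tolerability Assessment Tool (to be asked of primary surgeon at conclusion of surgery", covers whether movement was noticed, its severity, whether it interfered, and a rating of surgical conditions.
- The anesthesiologist's part, "Patient Movement Record (to be completed by anesthesiologist", has six numbered rows with columns for clinical scenario, BIS, major movement and interference.

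The Induction/maintenance list in the Intraoperative Protocol, which applies to both groups, names propofol twice: "Propofol bolus (0.2-0.5 mg/kg): as needed for patient movement" and "Propofol infusion started (25-50 mcg/kg/min". The second begins at drapes down, when isoflurane is stopped.

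On Data Collection: Intraoperative, propofol appears once, as a single milligram line under "Intraoperative Drug Totals".

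**The concern.** The outcome is defined by purpose: propofol given because the patient moved. The one field that collects propofol is defined by place, namely everything given during the case. The two agree only if no propofol is given for another reason, and the protocol itself specifies another reason for every patient.

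If the case total is used and includes the infusion, movement-related propofol is overstated in both arms and patients who never moved do not score zero. The proportion of patients needing any propofol for movement can then no longer be read from the total, and patients can be ranked wrongly.

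This matters because the protocol's own risk section names movement as the main hazard of omitting continuous relaxation and lists propofol first among the responses. The dose needed is a direct measure of what the experimental technique costs.

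**Working it through.** The plan states no figure for this item, so there is nothing to reproduce. The check sets the outcome against the form fields and then sizes the possible contamination.

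**1. Outcome items against the tolerability form.** Movement grade, interference, surgical conditions and BIS during movement each have a place on the form. The propofol dose is the only one of the five items without one.

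**2. Can the infusion be removed from the case total?** That needs rate × duration.

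- Rate: not recorded on any form. The protocol allows 25 to 50 mcg/kg/min.
- Start: drapes down has a row for TOF, temperature and BIS, but is absent from the clock-time table.
- Stop: the out-of-OR time is recorded.
- Result: chest closure to out of OR gives only an upper limit on the infusion's duration in the operating room.

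**3. Size of the infusion.** Dose in mg/kg = rate × minutes / 1000. The duration of 10 to 30 minutes is my assumption.

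| Minutes | At 25 mcg/kg/min | At 50 mcg/kg/min |
|---|---|---|
| 10 | 25 × 10 / 1000 = 0.25 | 50 × 10 / 1000 = 0.50 |
| 30 | 25 × 30 / 1000 = 0.75 | 50 × 30 / 1000 = 1.50 |

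One movement bolus is 0.2 to 0.5 mg/kg. In bolus equivalents:

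- 10 minutes: 0.25 / 0.5 = 0.5 to 0.50 / 0.2 = 2.5.
- 30 minutes: 0.75 / 0.5 = 1.5 to 1.50 / 0.2 = 7.5.

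**4. Uncertainty from the rate alone, with duration known exactly.** (50 − 25) × 10 / 1000 = 0.25 mg/kg, and (50 − 25) × 30 / 1000 = 0.75 mg/kg. That is 0.25 / 0.5 = 0.5 to 0.75 / 0.2 = 3.75 boluses.

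**5. Illustrative noise.** Take rate R uniform on 25 to 50 and time T uniform on 10 to 30, independent.

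- E[R] = 37.5 and E[T] = 20, so the mean is 750 mcg/kg = 0.75 mg/kg.
- E[R²] = 37.5² + 25²/12 = 1458.33, and E[T²] = 20² + 20²/12 = 433.33.
- Variance = 1458.33 × 433.33 − 750² = 69,444.
- SD = 263.5 mcg/kg, about 0.26 mg/kg, which lies within the range of a single bolus.

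**6. Example of misordering.** A patient who never moves, with 30 minutes at 50 mcg/kg/min, totals 1.50 mg/kg. A patient given three 0.2 mg/kg boluses, with 10 minutes at 25 mcg/kg/min, totals 0.60 + 0.25 = 0.85 mg/kg.

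**The case against.** The strongest reply is that the gap is an undefined field rather than a lost outcome. The Induction/maintenance list gives propofol no use before drapes down other than for movement. If staff leave the infusion out of the total, the milligram line is the outcome. This is correct, but no instruction says so, and a line for intraoperative totals is most naturally read as including the infusion.

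Second, the infusion instruction is the same in both arms. If its mean dose is equal, the difference in mean totals still estimates the difference in mean movement propofol, and only precision is lost. This stands for means. It does not rescue the dose within each arm, the proportion needing any, or a rank-based comparison. Nor is equality assured: surgeons and ICU providers are blinded, but the anesthesia team that gives the drugs is not listed as blinded.

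Third, the doses may be in the anesthesia record. They may, but the documents do not name it as a source for this item, and someone would still have to judge in retrospect which boluses were for movement. The clinical-scenario column could hold a dose as free text, but nothing asks for one.

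Fourth, the bolus equivalents pair opposite extremes over an assumed duration, and the SD is not set against any expected spread in movement propofol. That is fair. They show that the contamination can be as large as the quantity being measured, but they do not say how much precision is lost.

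Finally, the tables were read by a program. The TOF tables show only the eye site although the protocol also monitors the hand, so a column lost elsewhere cannot be fully excluded. The movement record's header and blank rows match, which makes a loss there unlikely.

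**Conclusion.** The concern holds, at minor severity. On the published forms this outcome cannot be derived as defined: the instrument that is meant to report it has no dose field, and the case total cannot be split between movement boluses and infusion.

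If the infusion is counted, it adds 0.25 to 1.5 mg/kg per patient under the assumed 10 to 30 minutes, with an illustrative SD of about 0.26 mg/kg under the uniform assumptions. The consequence is an overstated dose in both arms and a noisier comparison. Bias between arms is possible but not shown. The effect is confined to one of five items in a secondary outcome; the primary outcome and the sample size are untouched.

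**What to change.** - Add a column to the Patient Movement Record for the propofol bolus given in response to that movement, in mg. Allow continuation rows, since the form has six.
- Define the outcome as the sum of that column for each patient, excluding the drapes-down infusion, with 0 mg for a patient who received no movement bolus.
- State beside the propofol line on the intraoperative form whether the total includes the infusion, so that it is not mistaken for this outcome.

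The cost is one column on a form the anesthesiologist already completes for each movement, plus a line or two of wording. Treatment, visits and sample size do not change.
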